1. * Describe your plan to periodically evaluate the data collected regarding both harms and benefits to determine whether subjects remain safe. The plan might include establishing a data monitoring committee and a plan for reporting data monitoring committee findings to the IRB and the sponsor: The proposed study will use the FDA definition of adverse events (AE) and serious adverse events (SAE). Any SAE, which is unexpected and related to study intervention, will be reported immediately to the IRB and will be followed by an additional letter detailing the nature of the SAE. In the event that a participant either withdraws from the study or the investigators decide to discontinue a participant due to a SAE, the participant will be monitored by the co-PIs until (a) a resolution is reached (e.g., the problem has resolved or stabilized with no further change expected), (b) the SAE is determined to be clearly unrelated to the study intervention, or (c) the SAE results in death. Outcomes of SAEs will be regularly reported to the IRB and the sponsor. A summary of the SAEs that occurred during the previous year will be included in the annual progress report as well as in the annual IRB renewal.

If an unexpected adverse event occurs, the investigators will re-assess the risk-benefit ratio of the study and submit any modifications deemed necessary to the IRB for approval. If necessary, protocol refinement will occur to address safety concerns and/or adjustments necessary based on laboratory refinement, practitioner and/or patient acceptability, or other issues that may be uncovered.

Data will be continuously monitored by study coordinator and PI when subjects are being actively treated and are in the hospital. The PI and study coordinator will review questionnaire and cold-pressor data weekly.

- 2. * Describe your plan for sharing data and/or specimens:
 In the future, the investigators may decide to share data with other investigators both within and outside of this institution. If that were to occur, we would de-identify all of the information prior to sharing any data in this way.
- 3. If any research data is collected, stored, or shared in a paper format, address what precautions will be used to maintain the confidentiality of the data:

Paper-based records will be kept in a secure location, computer-based files will be available to personnel involved in the study through access

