Participants will receive ketamine infusion at the in-patient units. Should any complications associated with the medication occur, emergency cart is readily available at the units. Acute Interventional Perioperative Pain Service (AIPPS), which is responsible for the participants' postoperative pain management, is 24/7 available to address any associated issues.

All aspects of patients' analgesic care, including the management of low-dose ketamine infusion, will be administered under the consultation of the acute Interventional Perioperative Pain Service, which routinely uses these infusions in the managment of perioperative pain in opioid dependent or difficult to treat patients. This service is on call 24 hours/day. Ketamine infusions will only be administered to inpatients who are on floors where nursing staff has undergone training in the managment and administration of low dose ketamine infusions.

Patients will be instructed to notice the signs and symptoms of liver injury and report to medical staff about previous exposure to ketamine infusion. Patients will also be followed up for mental status change with Brief Psychiatric Rating Scale.

If the subject is particularly sensitive to the cold pressor test, they will be encouraged to move hand from the ice as soon as they feel any pain sensation. There is a four-minute limit on the test to reduce any risk of tissue damage. The participant will be made aware that they can refuse the cold pressor test should they choose.

Investigators who will access the identifiable medical records already have normal clinical access to all necessary records, as granted by the privacy office for job-related needs. Thus, only HIPAA trained research staff will be handling this information and this information will be stored in a locked

database protected by the UPMC firewall. Additionally, all data generated under this protocol will be monitored and maintained by the principal investigator. Any databases that contain identifiable information will be stored on a departmental drive on the UPMC network created for the principal investigator, and all data will be deidentified according to the HIPPA "safe harbor" guidelines prior to statistical analysis.

Pregnancy is being assessed via a medical record review. Since the ketamine infusion will occur for 48 hours while patient is in the hospital, there is little risk of becoming pregnant during study drug treatment period.

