The follow up contact will be made by trained physicians.

Financial ris	sks - will the subject or insurer be charged for any research
required pro	ocedures?
○ Yes ⊙	No

- 4. Describe the steps that will be taken to protect subjects' privacy:
 Research intervention will be conducted in a private room with the patient,
 collected information will be limited to that which is necessary for the goals
 of the research study, access to the patient's private information will be
 limited to those involved in the patient's medical care.
- 5. What steps will be taken in the event that a clinically significant, unexpected disease or condition is identified during the conduct of the study:
 - The patient's primary medical team will be immediately notified of the unexpected, clinically significant condition. The patient's clinically significant medical condition will be managed accordingly. If any of the clinically significant medical condition is related to the study, then the patient's participation in the study will be re-evaluated, with the possibility of the patient being withdrawn from the study if this leads to the resolution of the clinically significant medical condition
- 6. Describe the potential benefit that individual subjects may experience from taking part in the research or indicate if there is no direct benefit. Do not include benefits to society or others:
 Patients with chronic pain and opioid dependence may experience better analgesia in the postoperative period. There is no guaranteed direct benefit to participants.
- 7. Do you anticipate any circumstances under which subjects might be withdrawn from the research without their consent?

Ye	s 🖰	No
----	-----	----

- * Describe the circumstances and any procedures for orderly termination: Subject's failure to follow study procedures Severe allergic reaction to study drug
- 8. Describe procedures that will be followed when subjects withdraw from the research, including partial withdrawal from procedures with continued data collection and data already collected:

If a participant withdraws from research, follow up will cease but data previously collected may still be used in analysis.

View: Pitt SF: Placebo Arm

Placebo Arm

- 1. * Is there a commonly used diagnostic/treatment approach that is currently recognized as being effective for the proposed subjects' disease or condition, and that will be withheld from subjects assigned to the placebo arm of this research study:

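### A patient removed for a severe allergic reaction could lose the 10–14 day and 6-week outcomes, because withdrawal ends follow-up and stopping study drug is not separated from leaving the study

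*Protocol*

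**What the plan says.** The relevant text is in the protocol, under Risk and Benefits and under Data Safety and Monitoring. The SAP does not address withdrawal.

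- **Risk and Benefits, item 7.** The form asks for circumstances in which "subjects might be withdrawn from the research without their consent". The answer gives two: failure to follow study procedures, and "Severe allergic reaction to study drug".
- **Risk and Benefits, item 8.** The form asks for the procedures on withdrawal, "including partial withdrawal from procedures with continued data collection and data already collected". The whole answer is: "If a participant withdraws from research, follow up will cease but data previously collected may still be used in analysis".
- **Risk and Benefits, item 5.** For a study-related, clinically significant condition, participation is re-evaluated, "with the possibility of the patient being withdrawn from the study if this leads to the resolution of the clinically significant medical condition".
- **Data Safety and Monitoring, item 1.** If a participant withdraws, or "the investigators decide to discontinue a participant due to a SAE", then "the participant will be monitored by the co-PIs until (a) a resolution is reached", or until the event is judged clearly unrelated or ends in death.
- **Risk and Benefits, item 2.** The acute pain service oversees analgesic care, "including the management of low-dose ketamine infusion, will be administered under the consultation" of that service.

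**The concern.** A patient who reacts to the study drug needs the drug stopped. That is no reason to stop measuring the patient's outcomes. Item 7 describes the consequence of a severe reaction as leaving the research, and item 8 attaches the end of follow-up to leaving. The form's prompt about partial withdrawal with continued data collection is where the two could have been separated, and the answer does not take it up.

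The later outcomes are at stake. Study Aims item 2 says the pilot is to examine pain and opioid use six weeks after surgery and to support a larger trial. Study Design item 3 lists opioid use at 14 days and at 6 weeks within a primary outcome. It also lists post-surgical opioid analgesic efficacy as primary, and the only cold pressor test after surgery is at the 6-week visit. Removals for reaction to the study drug would probably fall in the ketamine arm, since the comparator is saline. Any resulting gap would therefore be related to treatment.

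**Working it through.** The plan gives no removal rate, dropout allowance or power calculation, so there is no figure to reproduce. The check is first textual and then a matter of scale.

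**1. Timing.** Research Activities item 1 runs the infusion to 48 hours after fascial closure. The next outcome visits are at 10–14 days and at about 6 weeks. A reaction during the infusion precedes both, so ending follow-up at that point loses both.

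**2. What each provision says about later outcomes.**

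| Provision | Trigger | Later outcome collection |
|---|---|---|
| Item 7 | Severe allergy to study drug; removal is possible, not automatic | Not mentioned |
| Item 8 | Withdrawal by a participant | Ends; earlier data may be used |
| Item 5 | Study-related condition, after re-evaluation | Not mentioned |
| Data Safety and Monitoring item 1 | Withdrawal, or discontinuation for an SAE | Safety monitoring only; no opioid, pain, questionnaire or cold pressor data named |
| Placebo Arm item 7 | Same stopping criteria in both arms; the criteria are not set out | Not mentioned |

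No provision distinguishes stopping the drug from leaving the study, or says that a patient taken off the infusion keeps the later visits.

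**3. Chance of a removal.** Inputs from the protocol are 20 subjects (Study Design item 1) and 1:1 allocation (Research Activities item 1), so about 10 per arm. The removal rate p per ketamine patient is my assumption. I take 0.1% to 2%, because Risk and Benefits item 1 lists allergic reaction as rare and item 7 requires a severe one.

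P(at least one removal) = 1 − (1 − p)^10

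- p = 0.1%: 1 − 0.999^10 = 1.0%
- p = 1%: 1 − 0.99^10 = 9.6%
- p = 2%: 1 − 0.98^10 = 18.3%

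Two or more removals at p = 2% has probability 1.6%.

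**4. Cost of one removal.** One patient in 10 is 10% of that arm's 14-day and 6-week data. In SD units, the 95% confidence interval half-width for a difference in means is t × √(1/n1 + 1/n2):

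- 10 v 10: 2.101 × 0.447 = 0.94 SD
- 10 v 9: 2.110 × 0.459 = 0.97 SD

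If the removed patient's 6-week outcome would have been d SD worse than the rest of the arm, the completers' mean is too favourable by (1/10) × d. With d assumed at 0.5 to 1, that is 0.05 to 0.10 SD, or 5% (0.05/0.97) to 10% (0.10/0.97) of the half-width. The documents do not link allergy to worse six-week pain or opioid use. If d is 0, only the small loss of precision remains.

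**5. Expected shift.** p × d runs from 0.001 × 0.5 = 0.0005 SD to 0.02 × 1 = 0.02 SD.

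**The case against.** The strongest reply is that item 8 speaks of a participant who withdraws. For someone who chooses to leave, ending follow-up and keeping earlier data is proper. Removal without consent is a separate question, and the item 7 answer says nothing about follow-up and only that removal might happen. This stands as a possible reading. It does not close the gap: item 8 is the only withdrawal procedure given, and if it does not apply to removal by the investigator, nothing says what happens to those patients' outcomes.

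A second reply is that the pain service can hold or stop the infusion without removing anyone from the study. That is also fair, although no text says such a patient stays in outcome collection. The consent form is listed but is not among the documents reviewed, so the absence is established only for the protocol and SAP.

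A third reply is that the trigger is narrow. Severe allergy is the only drug reaction item 7 names, known allergy or intolerance to ketamine is an exclusion, and the analysis is mainly descriptive. All of this stands, and it sets the size of the point.

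A reader might go further and infer that the plan turns drug intolerance in general into loss to follow-up. The documents do not say so. Confusion, drowsiness, hallucinations and mood change are listed as infrequent risks, but none is a stated reason for withdrawal. Item 5 requires re-evaluation first and mentions only a possibility.

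**Conclusion.** The point holds as a low-cost improvement. Read together, items 7 and 8 would remove a patient with a severe allergic reaction from the 10–14 day and 6-week assessments, including outcomes listed as primary. On the narrower reading of item 8, outcome follow-up after investigator-led removal is unspecified. Safety monitoring after an SAE continues and is not in question.

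The expected effect on this pilot is small: about a 1% to 18% chance of any removal in the ketamine arm, and 10% of that arm's later data for each one. This rests on about 10 patients per arm and an assumed removal rate of 0.1% to 2%. With no removals there is no effect.

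Two stronger inferences should be resisted. At removal rates of 5% or 10%, the same formula gives a 40% or 65% chance of at least one removal, but nothing in the documents supports rates that high for a severe form of an event called rare. Nor can it be said that inpatient opioid data would be lost. Research Activities item 1 takes them from the chart until discharge, so they are lost only if the end of follow-up is taken to stop chart abstraction as well. That matters for the 72-hour hydromorphone PCA measure, which Basic Information item 3 names as the primary outcome.

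**What to change.** Amend two answers in Risk and Benefits.

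1. **Item 7:** change severe allergic reaction from a reason for withdrawal from the research to a reason for permanently stopping study drug.
2. **Item 8:** add wording such as: *A subject whose study drug is stopped for any reason stays in the study. Chart opioid and pain data are collected to 72 hours or discharge, and the 10–14 day and 6-week visits take place, unless the subject withdraws consent to follow-up. Data collected before consent is withdrawn may be used.*

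The cost is one amendment to two form answers. No visit is added, because both visits and the 6-week payment are already planned. A subject's right to leave is unchanged, and so is the investigator's freedom to stop the drug for safety. The downside is that some patients who had a reaction may decline to return, so the change reduces this missing data but cannot rule it out.

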STUDY: Perioperative Ketamine in Opioid-Tolerant Patients Undergoing Lumbar Spine Surgery: A

Randomized, Double-blind, Place-controlled Trial

Principal Investigator: [name], PhD, MBA

IRB: STUDY19020144

NCT: 04220489

Statistical Analysis Plan – Approved 09/03/2019

This is a pilot to support a P01 program pilot application to the NIH, so the data will be analyzed mainly using descriptive statistics. Additional statistical analysis methods such as a 2-sample t test to compare significance between groups may also occur.

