STUDY: Perioperative Ketamine in Opioid-Tolerant Patients Undergoing Lumbar Spine Surgery: A

Randomized, Double-blind, Place-controlled Trial

Principal Investigator: [name], PhD, MBA

IRB: STUDY19020144

NCT: 04220489

Study Protocol – Approved 09/03/2019

Basic Information

1. * Title of study:

Perioperative Ketamine in Opioid-Tolerant Patients Undergoing Lumbar Spine Surgery: A Randomized, double-blind, placebo-controlled trial

2. * Short title:

Perioperative Ketamine in Opioid-Tolerant Patients Undergoing Lumbar Spine Surgery

3. * Brief description:

The goal of this study is to determine whether comprehensive perioperative administration of the NMDA receptor antagonist ketamine can increase postoperative pain tolerance and reduce opiate consumption in chronic back pain patients undergoing spinal laminectomy/fusion when compared to placebo

Design: Prospective, Randomized, Double-Blind, Placebo Controlled trial involving opiate-dependent patients undergoing lumbar spine surgery. Opioid dependence will be defined as greater than 60 mg oral morphine equivalents/day for greater than one week. Intraoperatively, patients will receive a 1 mg/kg dose of intravenous ketamine or saline with 15 minutes after induction of general anesthesia. Thereafter, a continuous infusion of 0.20 mg/kg/hr ketamine with a maximum dose of 20 mg/hr or saline will be run to conclude at 48 hours after the end of the surgery (fascial closure). The primary outcome measure will be hydromorphone PCA usage during the first 72 hours postoperatively. Secondary outcome measures will be VAS pain scores at rest and with movement in PACU, 24 hr, 48 hr, 72 hr, 2 week (post-op visit), 6 week follow-up visit, as well as, McGill Pain Questionnaire, Pain Catastrophizing Scale, and emotional distress surveys assessing depression and anxiety at preop/screening, postop and 6 week follow-up (PROMIS Emotional Distress-Anxiety Short Form, PROMIS Emotional Distress-Depression Short Form), as well as a Neuro-QOL Short Form v1.1 - Satisfaction with Social Roles and Activities.

4.	* Principal investigator:
	[name]

5 .	*	Does	the	investigator	have a	financial	interest	related	to this	researd	:h?
	- 0	Ye	s 💿	No							

6. * Will an external IRB act as the IRB of record for this study?

O Yes No

- 7. * What kind of study is this? Single-site study
- 8. Attach the protocol:
 - Sponsor/Multicenter protocol
 - Investigator-initiated protocol
 - Emergency Use Consent/ Protocol/ FDA Form 3926

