This medical record review to identify eligible candidates is minimal risk and that the rights and welfare of subjects will not be adversely affected The primary surgeon will identify patients who are prescreened via medical record to be eligible for inclusion, ask them if they would be interested in participating, and if so, the enrollment and consent process would be initiated. Participating neurosurgeons include Drs. [name], who will identify eligible patients. Informed consent will be performed by this Neurosurgeon, the PI, or other co-investigator in the study. Enrollment will be performed by the study coordinator and/or trained representative from the Acute Interventional Perioperative Pain Service (AIPPS). Enrollment will include review of eligibility, and detailed explanation of the study.

5. * Describe all compensation/incentives offered to participants and timing of these offers:

Participants will be compensated up to \$100 for travel and parking expenses related to Pre-Op Visit (\$50) and 6-Week Follow-up visit (\$50)

Recruitment materials: (attach all material to be seen or heard by subjects, including advertisements and scripts)

Document Category Date Modified Document History

There are no items to display

View: Pitt SF: Study Design

Study Design

1. Total number of subjects to be enrolled at this site (enter -1 for chart reviews, banking, registries):
20

2. Describe and explain the study design:

This study is being proposed as a pilot study to inform the feasibility and direction of a larger P01 NIH funded trial.

3. Describe the primary and secondary study endpoints:

Primary Outcome measure:

- ¬ Pre- and post-surgical pain rating
- \neg Pre- and post-surgical opioid utilization (in morphine equivalent units in the PACU and post-operative period until discharge, at 14 days, and at 6 weeks follow-up)
- ¬ Pre- and post-surgical opioid analgesic efficacy

Secondary outcome measures:

- ¬ Mcgill Pain Questionnaire-Short Form
- ¬ Pain Catastrophizing Scale
- ¬ PROMIS Emotional Distress-Anxiety Short Form
- ¬ PROMIS Emotional Distress-Depression Short Form
- ¬ Neuro-QoL Short Form v1.1 Satisfaction with Social Roles and Activities
- ¬ Cold Pressor Test

4. Provide a description of the following study timelines:

Duration of an individual subject's active participation:

6 weeks

Duration anticipated to enroll all subjects:

5 months

Estimated date for the investigator to complete this study (complete primary analyses):

10/31/2019

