5. List the inclusion criteria:

Patients undergoing lumbar spine surgery of at least one level, and no more than 4 levels.

Patients with chronic back pain (>3 months)

ASA 1-3

Age 18-65

Opiate-dependent, meeting both of the following criteria:

- 1.Daily opiate use for at least 2 months
- 2. Oral morphine equivalent of 60 mg/day or higher

- 6. List the exclusion criteria:
 - -Intolerance or known allergy to ketamine
 - -History of increased intraocular pressure (> 22mmHg)
 - -Uncontrolled hypertension (systolic blood pressure greater than or equal to 180, diastolic blood pressure greater than equal to 100)
 - -Increased intracranial pressure (signs including:Behavior changes, Decreased consciousness, Headache, Letharqy
 - -Neurological symptoms, including weakness, numbness, eye movement problems, and double vision, seizures, vomiting)
 History of psychosis

Pregnancy

Patients with significant liver disease (signs and symptoms of liver injury, such as discolored skin and eyes that appear yellowish, abdominal pain and swelling, Itchy skin that doesn't seem to go away, Dark urine color, Pale stool color, Bloody or tar-colored stool, Chronic fatigue, Nausea, Loss of appetite, with or without elevated LFTs: AST > 120 IU/ml, AP >130 IU/ml, and ALT >40 IU/ml)

- -Patients with exposure to CYP3A and / or CYP2B6 inhibitors, including the herbs and the over-the-counter compounds (list of drugs can be found at http://www.fda.gov/drugs/developmentapprovalprocess/developmentresources/druginteractionslabeling/ucm093664.htm)
- 7. Will children or any gender, racial or ethnic subgroups be explicitly excluded from participation?
 - Yes No
 - * Identify the subgroups and provide a justification: Presbyterian Hospital is an adult-only facility
- 8. Describe the power analysis used and cite your method of statistical analysis. If a power analysis is not possible, thoroughly justify the sample size required for the study, including appropriate literature citation (alternatively provide page reference in attached protocol):

 This is a pilot to support a P01 program pilot application to the NIH, so the data will be analyzed mainly using descriptive statistics. Additional statistical analysis methods such as a 2-sample t test to compare significance between groups may also occur.

View: Pitt SF: Research Activities

Research Activities

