1. * Provide a detailed description of all research activities (including screening and follow-up procedures) that will be performed for the purpose of this research study. This description of activities should be complete and of sufficient detail to permit an assessment of associated risks. Patients will be recruited from the UPMC Neurosurgery Clinic. The primary surgeon will identify patients who would be eligible for inclusion, ask them if they would be interested in participating, and if so, the enrollment and consent process would be initiated. The participating neurosurgeon is [name], who has agreed to allow us access to his patients. Informed consent will be performed by [name], or the Pl. Enrollment will be performed by the study coordinator and/or trained representative from the Acute Interventional Perioperative Pain Service (AIPPS). Enrollment will include review of eligibility, and detailed explanation of the study.

Screening Visit: Approximately 1 hour

After patients are enrolled into the study at the preoperative neurosurgery clinic, a number of forms will filled out by the subjects: McGill Pain questionaire-Short form (measures pain), pain medication review form, and the Pain Catastrophizing Scale (PCS) (assesses patient's ability to tolerate pain) PROMIS Emotional Distress-Anxiety Short Form (measures anxiety) and PROMIS Emotional Distress-Depression Short Form (measures depression), Brief Psychiatric Rating Scale (assesses psychiatric state of patient) and Neuro-QoL Short Form v1.1 - Satisfaction with Social Roles and Activities (assesses depression/anxiety when it comes to social roles) will also be completed.

Pre-Operative Visit: Approximately 1.5 hrs

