The subject will be asked to come into the [name] on a date after the clinic visit but before their day of surgery for a Pre-Operative Visit. Investigators will work with the subject to determine their opioid dose regimen, and the subject will be asked to come into the Aiken Medical Building thirty minutes before their opioid dose is due and will be asked to bring with them their upcoming dose of pain medication. Prior to taking their pain medication, the subject will then be administered a coldpressor pain sensitivity test. For this test, the subject will place their nondominant hand in a bowl of ice water up to the wrist. Pain threshold is defined as the time in seconds that is takes for the subject to first report the sensation of pain in the immersed hand. Pain tolerance is defined as the time in seconds that it takes for the subject to withdraw their hand from the ice water because it has become too uncomfortable for them to keep their hand immersed any longer. A cut-off of four minutes will be imposed to limit the potential for any tissue damage. At this time, the subject will be asked to remove their hand from the ice water, even if they say that they could keep their hand immersed for longer. Pain threshold, tolerance and cut-off will be recorded using a stop watch. Heart rate and blood pressure

will be recorded before and after the cold-pressor test. Once the cold pressor test is completed, the McGill Pain Questionnaire will be administered. After this questionnaire is complete, the subject will take the dose of opioid medication they have brought from home and are scheduled to receive and will wait in the clinic for 30 minutes for the pain medication to take effect. Once the 30 minutes is complete, the cold-pressor test will be repeated, heart rate and blood pressure collected before and after, and McGill Pain Questionnaire will be administered again. Opioid-analgesic efficacy will be estimated by the change in pain threshold and tolerance observed after the opioid was consumed relative to initial assessment of pain threshold and tolerance. The subject will be compensated \$50 for this pre-operative visit.

Surgical Visit:

Study groups:

Patients will be randomized to one of the following groups:

- 1. Intraoperative ketamine- post operative 48 hr ketamine infusion
- 2. Intraoperative placebo (saline)- post operative placebo (saline) infusion

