6-Week Follow-Up Visit: Approximately 1.5 hours

The subject will be asked to come to the [name] approximately 6 weeks after their surgery for a 6-Week Follow-Up Visit. Investigators will work with the subject to determine their post-operative opioid dose regimen, and the subject will be asked to come in for the visit thirty minutes before their opioid dose is due and bring with them their upcoming dose of pain medication. Prior to taking their pain medication, the subject will then be administered a cold-pressor pain sensitivity test, in a manner identical to that use during the pre-operative assessment.In addition to the McGill Pain Questionnaire-Short form, a pain medication review form, the Pain Catastrophizing Scale (PCS) (Sullivan, 1995), the PROMIS Emotional Distress-Anxiety Short Form, the PROMIS Emotional Distress-Depression Short Form, Brief Psychiatric Rating Scale and Neuro-QoL Short Form v1.1 - Satisfaction with Social Roles and Activities will also be completed. The subject will be compensated \$50 for this 6-week follow-up visit.

Upload a copy of all materials used to collect data about subjects: (Attach all surveys, interview/focus group scripts, and data collection forms except for case report forms, SCID or KSADS):

	Document	Category	Date Modified	Document History
View	Brief Psychiatric Rating Scale (0.01)	Data Collection	3/6/2019	History
View	PROMIS v1.0 ED-Depression Short Form 1.pdf(0.01)	Data Collection	3/6/2019	History
View	PROMIS v1.0 ED-Anxiety Short Form 1.pdf(0.01)	Data Collection	3/6/2019	History
View	Pain%20catastrophizing%20scale-1.docx(0.01)	Data Collection	3/6/2019	History
View	Neuro-QOLv1.1- SatisfactionwithSocialRolesandActivitiesSF 03-06- 2014.pdf(0.01)	Data Collection	3/6/2019	History
View	Medications- questionaire.doc(0.01)	Data Collection	3/6/2019	History
View	Mcgill pain questionaire.docx(0.01)	Data Collection	3/6/2019	History

3. * Will blood samples be obtained for research purposes?

○ Yes [©] No

View: Pitt SF: Consent Process

Consent Process

Enter N/A in response to the following questions if a Waiver of Consent is requested for all research activities or if no subjects are being enrolled.

1. * Indicate where the consent process will take place and at what point consent will be obtained:

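### The plan names only an optional 2-sample t test and specifies no use of the preoperative values it collects; adjusting for one baseline covariate would be a cheap improvement

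*SAP*

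**What the plan says.** The SAP consists of two sentences, and Protocol, Study Design item 8 has the same two. The first makes the analysis mainly descriptive because this is a pilot. The second is "Additional statistical analysis methods such as a 2-sample t test to compare significance between groups may also occur". No covariate, change-score rule or transformation is named anywhere.

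The preoperative values are collected all the same:

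- **Screening** (Research Activities item 1): "a number of forms will filled out by the subjects: McGill Pain questionaire-Short form (measures pain), pain medication review form". The other four questionnaires listed as secondary outcomes are also completed there.
- **Pre-operative visit:** the opioid regimen is established and cold-pressor tests are run before and after a dose. "Opioid-analgesic efficacy will be estimated by the change in pain threshold and tolerance observed after the opioid was consumed", and "A cut-off of four minutes will be imposed to limit the potential for any tissue damage".
- **6-week visit:** the cold-pressor test is done "in a manner identical to that use during the pre-operative assessment".

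Study Design item 3 describes each of its three primary outcomes as covering the time both before and after surgery. Opioid use is to be measured "in morphine equivalent units in the PACU and post-operative period until discharge, at 14 days, and at 6 weeks follow-up". Basic Information item 3 gives a different primary outcome: "The primary outcome measure will be hydromorphone PCA usage during the first 72 hours postoperatively". Entry requires "Oral morphine equivalent of 60 mg/day or higher" (Study Design item 5).

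**The concern.** Enrolment is 20, so 10 per arm if all are randomized and complete. At that size the interval around any difference between arms is wide, and a preoperative measurement of the same quantity is the cheapest way to narrow it. The data will exist, but the plan does not say whether arms are compared on the postoperative value, the change, or an adjusted value, nor on what analysis scale for opioid totals. An analyst could choose among these after seeing the results.

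At stake are the precision of each estimate and the choice of model being fixed in advance. Fixing the model does not settle which of the many outcomes are compared, and it does not deal with multiplicity.

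**Working it through.** **Inputs from the documents.** N = 20 (Study Design item 1), 1:1 allocation (Research Activities item 1), so n = 10 per arm. The enrolment figure rests on no stated alpha, power, effect size or SD, so there is no sample-size calculation to reproduce. **Assumed:** two-sided 5%, the baseline-outcome correlation ρ, and all distribution shapes.

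**1. Unadjusted t test.** Half-width of the 95% CI, in outcome SDs: t(18) × √(2/10) = 2.101 × 0.447 = 0.940.

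**2. ANCOVA with one covariate.** The variance is multiplied by (1 − ρ²)(1 + 1/16). The 1/16 is the average cost of chance baseline imbalance, 1/(N − 4). Half-width: 2.110 × 0.447 × √[(1 − ρ²) × 1.0625].

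| ρ | Half-width (SD) | Versus 0.940 | Simulated (40,000 replicates) |
|---|---|---|---|
| 0 | 0.973 | +3.5% | +3.3% |
| 0.3 | 0.928 | −1.3% | −1.4% |
| 0.5 | 0.842 | −10.4% | −10.4% |
| 0.7 | 0.695 | −26.1% | −26.2% |

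Break-even is at ρ of about 0.25. These figures suit the questionnaires, which have no entry floor.

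**3. Fewer completers.** With 8 per arm, simulated half-widths are 1.102 against 1.055 at ρ = 0 (+4.5%), 1.049 against 1.052 at 0.3 (−0.3%), 0.954 against 1.054 at 0.5 (−9.5%) and 0.786 against 1.053 at 0.7 (−25.4%). Break-even moves to about 0.3.

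**4. Change scores.** If the SD is the same before and after, a change score has (2 − 2ρ) times the variance of the postoperative value. It beats a post-only comparison only if ρ exceeds 0.5. At ρ = 0.5 the ratio is 1.00, against 0.75 × 1.0625 = 0.797 for ANCOVA; at 0.7 it is 0.60 against 0.51 × 1.0625 = 0.542.

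**5. Opioid totals.** The 60 mg/day floor truncates the baseline dose and weakens the correlation: ρ′ = ρu / √(1 − ρ² + ρ²u²), where u² is the fraction of baseline variance that remains. For a floor at the median of a normal (log) dose, u² = 1 − 2/π = 0.363 and u = 0.603. At ρ = 0.5 this gives 0.301/√(0.75 + 0.091) = 0.33. Where the floor cuts is not stated, so three positions are shown, with simulated CI change:

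| ρ without floor | Floor at 25th percentile | 50th | 75th |
|---|---|---|---|
| 0.3 | ρ′ 0.22, +0.7% | 0.19, +1.6% | 0.15, +2.1% |
| 0.5 | 0.39, −4.8% | 0.33, −2.4% | 0.27, −0.6% |
| 0.7 | 0.58, −16.0% | 0.51, −11.0% | 0.43, −6.9% |

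ANCOVA null rejection was 4.7-5.1%.

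**6. Opioid analgesic efficacy.** The within-visit change was simulated with the four-minute cap reached in 3-44% of patients. The correlation between visits was 0.09-0.51, the CI ran from 2% wider to 14% narrower, and null rejection was 4.3-4.9%.

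**7. Analysis scale for opioid totals.** t-test power for a 50% reduction, raw against log: 45% against 55% if log-normal with CV 0.8; 38% against 36% if gamma with CV 0.8; 94% against 85% if near-normal with CV 0.4. Neither scale is better throughout.

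**The case against.** The strongest reply is that this is a pilot with a mainly descriptive analysis, that the t test is optional and only an example, and that it is valid. That stands, and it is why the point is minor. The proposal applies only where arms are compared, which the SAP itself allows.

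Several stronger readings are tempting, and the documents do not support them:

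- **That the plan ignores baseline.** The primary outcomes are framed as before and after surgery, efficacy is defined as a change, and a t test on change scores is not excluded. What can be said is that no use of baseline is specified.
- **That opioid totals have no scale.** The unit is set: morphine equivalents, and per 24 hours at the 10-14 day visit. Only the analysis scale is open.
- **That the log scale should be required.** It loses power under gamma or near-normal totals. It also does not carry over simply to 14 days and 6 weeks, where use may be zero.
- **That the pilot's interval or SD will be used to size the larger trial.** Study Design item 2 speaks of feasibility and direction, and no text names these as planning inputs.

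It is also fair that the gain depends on correlations nobody has supplied, and that for opioid totals it is small unless the correlation is high.

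**Conclusion.** The concern holds in a limited form. The only named between-arm method is an optional t test, and the plan does not say how the preoperative values enter a comparison. The t test is not wrong; it may be inefficient.

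The gain is worthwhile for questionnaire scores if ρ is 0.5 or more, and uncertain for efficacy. For opioid totals it is little or none at ρ of 0.3 to 0.5. The loss is bounded at about 3% in CI width with 10 per arm and about 4.5% with 8. These sizes rest on assumed correlations, approximate normality and one covariate per outcome; adjusting for every baseline measure at once would not be realistic with 20 patients.

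**What to change.** First reconcile the opioid outcome in Basic Information item 3 with that in Study Design item 3. Then keep the descriptive presentation and replace the t-test sentence, in the SAP and in Study Design item 8, with:

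> Where arms are compared, the estimate is a baseline-adjusted difference (ANCOVA with arm and one covariate, the preoperative value of the same measure) with 95% CI; the unadjusted comparison is a sensitivity analysis.

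Name the covariate for each outcome:

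- **Questionnaires at 10-14 days and 6 weeks:** the screening score of the same instrument. Screening is the one preoperative visit with all five, and the McGill forms at the pre-operative visit are timed around a dose.
- **Pain rating:** a preoperative rating of the same kind, where one exists. Research Activities describes the 0-10 rating only for the hospital stay.
- **Opioid use in hospital, at 14 days and at 6 weeks:** preoperative morphine equivalents per day from one named source. The record review, the screening form and the pre-operative visit are all candidates.
- **Opioid analgesic efficacy at 6 weeks:** the same measure from the pre-operative visit, if the post-dose test is repeated. Flag values at the cap, and report how many patients have no result.

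A log-scale ratio for in-hospital opioid totals may be offered as an option.

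The cost is SAP wording, a few lines of code and one degree of freedom (18 to 17). No new data are needed.
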